13.2 Data Analysis

As a phase I trial to evaluate the preliminary data on the safety and immunogenicity of a neoantigen peptide vaccine strategy, the data analysis for this study is descriptive in nature. Demographic and clinical characteristics of the sample, toxicity by grade, as well as response and time to toxicity will be listed and summarized using descriptive statistics.

13.2.1 Primary objective: safety analysis

Toxicity evaluation is the primary objective of this trial. The data will be descriptive, and standard toxicity definitions and criteria will be used as outlined in the National Cancer Institute Common Terminology Criteria for Adverse Events version 5.0.

Since enrollment will be concurrent with the first dose of the personalized pancreatic cancer DNA vaccines, all subjects will have received at least one vaccination, and all subjects will provide at least some safety data.

The number and percentage of subjects experiencing each type of adverse event will be tabulated by severity, and relationship to treatment. If appropriate, confidence intervals will be used to characterize the precision of the estimate. A complete listing of adverse events will also be tabulated, and will provide details including severity, relationship to treatment, onset, duration, and outcome.

Laboratory data measured on a continuous scale will be characterized by summary statistics (mean and standard deviation). Boxplots of laboratory data will be generated for baseline values and for values measured during and after protocol therapy at each specific time point. Each boxplot will show the median, 1st and 3rd quartiles. Outliers will be individually plotted in a separate graph, as appropriate.

13.2.2 Secondary objective: immune response as measured by ELISPOT analysis and multiparametric flow cytometry

Immune response as measured by ELISPOT analysis and multiparametric flow cytometry is the secondary objective of this trial. The frequency of antigen-specific T cells at each time will be summarized using means, standard deviations and medians, and the change over time will also be compared using two-ANOVA for repeated measurement data or Friedman rank-sum test as appropriate. The immunogenicity of the neoantigen peptide vaccine will also be analyzed qualitatively by summarizing the phenotypic and functional characteristics of antigen-specific T cells. Responses will be considered positive if the number of T cells after vaccination is greater than two standard deviations above the mean before vaccination [50]. The frequency of positive responses at each time point will be assessed and binomial response rates with 95% confidence interval estimates will be presented. In addition to presenting the binomial response rates, graphical and tabular summaries of the underlying distributions will be made.

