1.1 Primary objective

The primary objective is to assess the safety and feasibility of the neoantigen peptide vaccine approach. This trial will be considered feasible if we are able to successfully perform tumor/normal exome sequencing, identify at least 3 neoantigens per patient, and manufacture and administer neoantigen vaccines to more than 50% of enrolled patients.

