4.2 Registration procedures

Patients must not start any protocol intervention prior to registration through the Siteman Cancer Center.

Registration for this trial will be a two-step process. Step 0 will be screening and confirmation of eligibility for vaccine creation. Step 1 will be screening and confirmation of eligibility for vaccine administration. See Section 3: Patient Selection for eligibility criteria for each step and Section 8: Study Calendar for screening procedures for each step.

Step 0 screening must occur within 16 weeks of surgical resection, and Step 0 enrollment can occur up to four weeks after initiation of adjuvant chemotherapy. Step 1 screening will occur when the patient's vaccine is ready or nearly ready, but must be within 14 days of the first vaccine administration.

The following steps must be taken before registering patients to this study:

- (1) Confirmation of patient eligibility by Washington University (applies to both Step 0 and Step 1)
- (2) Registration of patient in the Siteman Cancer Center database (This will be done by Washington University research coordinator. Step 0 enrollment will be "On Study" in the OnCore database, and Step 1 enrollment will be "On Treatment" in the OnCore database.)
- (3) Assignment of unique patient number (UPN)

Once the patient has been entered in the Siteman Cancer Center OnCore database, the WUSM coordinator will forward verification of enrollment and the UPN via email.

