6.3 Definitions of Evaluability

All enrolling patients are evaluable for the primary objective of feasibility, even patients whose tumor/normal exome sequencing is not completed or who are unable to have vaccine manufactured or administered.

A patient must have received at least one injection of vaccine in order to be evaluable for the primary objective of safety and the secondary objective (prevalence of antigen-specific T cells in peripheral blood).

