8 STUDY CALENDAR

The window for Step 0 screening procedures is up to 28 days prior to enrollment. Enrollment must occur within 28 days of the patient starting on adjuvant therapy. The window for Step 1 screening procedures is 14 days prior to first vaccine dose.

	Step 0 Screening	Step 1 Screening	Day 1	Day 4 ^f	Day8 ^f	Day15 ^f	Day 22 ^f	Day 50 (+/-2wk)	Day 78 (+/-2wk)	EOT	F/U ^h
Neoantigen peptide vaccine ^{a,i}			X	X	X	X	X	X	X		
Informed consent	X										
Demographics	X										
Medical history	X										
Physical exam	X	X	X	X	X	X	X	X	X	X	X
Concurrent Meds	X ----- X										
Vital signs	X	X	X	X	X	X	X	X	X		X
Height	X										
Weight	X	X	X	X	X	X	X	X	X		X
Performance Status	X	X	X	X	X	X	X	X	X		
CBC w/diff, plts	X	X	X				X	X	X		
CMP ^b	X	X	X				X	X	X		
INR, PTT	X	X									
EKG	X	X									
Radiologic evaluation	Radiologic measurements will be performed as clinically indicated. Documentation of tumor recurrence or metastatic disease must be provided for patients removed from study for progressive disease.										
Adverse event evaluation			X ^g	X ^g	X ^g	X ^g	X ^g	X ^g	X ^g	X	X
B-HCG	X ^e	X ^e	X ^e	X ^e	X ^e	X ^e	X ^e	X ^e	X ^e		
Immune monitoring ^c	X		X				X	X	X		X ^j
Pathology Review ^d	X										
Eligibility Confirmation	X	X									

a: Personalized synthetic long peptide pancreatic cancer vaccine

b: Albumin, alkaline phosphatase, total bilirubin, bicarbonate, BUN, calcium, chloride, creatinine, glucose, LDH, phosphorus, potassium, total protein, SGOT [AST], SGPT [ALT], sodium.

c: Immune monitoring labs to consist of seven 10mL green top heparin tubes for isolation of PBMCs. During adjuvant therapy, the mid and end of chemo draws are optional. Generally, these should occur at a clinic visit associated with the restaging scan, as well as at each follow up visit. This will yield approximately 50-200 x10⁶ PBMCs per collection.

d: Pathology review to confirm diagnosis of adenocarcinoma and evaluate tumor cellularity.

e: Serum or urine pregnancy test (women of childbearing potential).

f: +/- 1 days with at least 24 hours between vaccinations

g: Adverse event evaluation on day of vaccine

h: ± 28 days; follow-up or telephone contact at 4 weeks and 1 year after last injection and annually thereafter if the patient is alive and available for follow-up. F/U visits may be done at the participant's local MD office.

i: patients may discontinue participation if vaccine production is unable to be completed

j: optional based on patient availability

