13 STATISTICAL CONSIDERATIONS

13.1 Experimental Design

This is a phase 1, open-label, trial of a neoantigen peptide vaccine strategy. Twenty patients who have had an R0/R1 surgical resection, and who have completed adjuvant chemotherapy will be enrolled. At our institution, pancreatic cancer patients undergo routine staging during (three months) and after adjuvant chemotherapy. If there is no evidence of disease, patients will be eligible for enrollment. After enrollment, exome sequencing of tumor/normal DNA and cDNA-capture sequencing of the tumor will be performed to identify somatic mutations present in the tumor and confirm expression of these mutations at the mRNA level. Epitope prediction algorithms will then be used to prioritize neoantigens for inclusion in neoantigen peptide vaccines, and the neoantigen peptide vaccines will be designed and manufactured. The neoantigen peptide vaccines will be administered starting two to four weeks after the completion of adjuvant chemotherapy. The neoantigen peptide vaccines will be administered at seven time points, Days 1, 4, 8, 15, 22, 50, and 78.

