14 DATA MANAGEMENT

Data collected will be collected using paper case report forms or OnCore electronic data capture forms. Forms must be completed within 28 days of time point.

Case report forms with appropriate source documentation will be completed according to the schedule listed in this section.

Case Report Form	Submission Schedule
Original Consent Form	Prior to registration
Registration Form Eligibility Form Demographics Form On-Study Form Medical History Form	Prior to starting treatment
Physical Exam Form	Enrollment Mid chemo End of chemo Day 1 Day 4 Day 8 Day 15 Day 22 Day 50 Day 78 4 weeks after last injection 1 year after last injection
Vaccine Administration Form	Day 1 Day 4 Day 8 Day 15 Day 22 Day 50 Day 78
Immune Monitoring Form	Enrollment Mid chemo End of chemo Day 1 Day 22 Day 50 Day 78
Imaging Form	Mid chemo End of chemo
Toxicity Form	Day 1 Day 4 Day 8 Day 15 Day 22 Day 50 Day 78
Concomitant Medications Form	Continuous through Week 25
Follow Up Form	4 weeks after last injection 1 year after last injection Year 2 and annually thereafter
Death Form	Time of death
Progression Form	Time of disease progression
MedWatch Form	See Section 11.0 for reporting requirements

Any queries generated by Washington University must be responded to within 28 days of receipt by the participating site. The Washington University research team will conduct a regular review of data status at all secondary sites, with appropriate corrective action to be requested as needed.

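### The plan gives two enrolment totals (15 and 20) and conflicting enrolment times, although the primary feasibility criterion is a proportion of enrolled patients

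*Combined protocol and SAP*

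**What the plan says.** **Criterion and population.** Section 1.1 makes feasibility part of the primary objective. It asks for sequencing, at least 3 neoantigens per patient, and the ability to "manufacture and administer neoantigen vaccines to more than 50% of enrolled patients". Section 6.3 sets the population: "All enrolling patients are evaluable for the primary objective of feasibility, even patients whose tumor/normal exome sequencing is not completed". It goes on to include patients for whom no vaccine is made or given. Safety and immunogenicity need at least one injection.

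**When patients enrol.**
- Section 4.2: "Step 0 enrollment can occur up to four weeks after initiation of adjuvant chemotherapy". It also names a later Step 1 enrolment, recorded as on treatment, with Step 1 screening within 14 days of the first dose.
- Section 8: "Enrollment must occur within 28 days of the patient starting on adjuvant therapy".
- Section 14, form schedule: "Enrollment Mid chemo End of chemo Day 1".
- Section 13.1: "Twenty patients who have had an R0/R1 surgical resection, and who have completed adjuvant chemotherapy will be enrolled", and then "After enrollment, exome sequencing of tumor/normal DNA and cDNA-capture sequencing of the tumor will be performed".
- Section 13.2.1: "Since enrollment will be concurrent with the first dose of the personalized pancreatic cancer DNA vaccines, all subjects will have received" at least one vaccination.

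**How many.** The Summary enrols fifteen and Section 13.1 twenty. Sections 13.1.1 to 13.1.3 work with 15 evaluable patients. Section 6.1 replaces patients whose vaccine cannot be produced. Section 13.1.1 replaces those it describes as failing screening because of sequencing problems.

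**The concern.** A criterion stated as a proportion of enrolled patients needs a fixed meaning of enrolled and a planned number. Here the word refers to three different moments: early in chemotherapy (4.2, 8, 14), after chemotherapy but before sequencing (13.1), and at the first dose (13.2.1). The choice decides whether patients lost to failed sequencing, failed manufacture or recurrence are in the denominator.

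The replacement rules add to this. Sequencing follows Step 0 enrolment, yet Section 13.1.1 calls sequencing losses screen failures. Some may be true failures before enrolment, since tumour cellularity is an inclusion criterion checked by pathology review at Step 0. Neither replacement rule says that a patient replaced after Step 0 enrolment still counts under 6.3.

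Section 13.2 then names toxicity as the primary objective and has no sentence reporting the feasibility proportion, so the statistical section does not settle the question.

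**Working it through.** **1. Which number the calculations use.**
- Safety (13.1.2): Pr(0 events) = (1 − p)^n. At p = 0.15 and n = 15, 0.85^15 = 0.087, as printed, so the chance of at least one event is 0.913, matching the stated figure of more than 90%. With n = 20 it would be 0.85^20 = 0.039.
- At p = 0.035, the exact chance of two or more events is 0.095 for n = 15 (printed 0.100) and 0.154 for n = 20.
- Immunogenicity (13.1.3): one-sided paired t-test, alpha 0.05, increase of 0.68 SD, taking the SD of the change equal to SD (correlation 0.5). Power is 80.5% for n = 15, against the stated 80%, and 90.1% for n = 20.

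The stated figures therefore rest on 15 evaluable patients. The twenty in 13.1 enters no calculation.

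**2. Timing side by side.**

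| Section | Enrolment happens | Can an enrolled patient go unvaccinated? |
|---|---|---|
| 4.2, 8 (Step 0) | within 28 days of starting adjuvant therapy | yes |
| 6.3 | not dated | yes, explicitly |
| 13.1 | after chemotherapy, before sequencing | yes |
| 13.2.1 | at the first dose | no |

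Section 3.3 requires at least 4 months of adjuvant chemotherapy before vaccination. Four months less at most 4 weeks leaves about three months between Step 0 enrolment and the first dose. The two events are not concurrent.

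**3. What the criterion requires.**
- 15 enrolled: more than 7.5, so at least 8 successes.
- 20 enrolled: more than 10, so at least 11.
- Replacement until 15 are vaccinated, with N enrolled at Step 0: 15/N > 0.5 requires N ≤ 29. 15/29 = 51.7% meets the criterion; 15/30 = 50.0% does not.

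**4. How the proportion moves.** Illustrative totals with 15 vaccinated, exact (Clopper-Pearson) 95% intervals:
- 18 enrolled: 15/18 = 83% (59% to 96%).
- 20 enrolled: 15/20 = 75% (51% to 91%).

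A vaccinated patient has necessarily been sequenced. The condition of at least 3 neoantigens could lower the numerator further.

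**5. Would the verdict change?** Section 2.8 gives more than 85% for past design and manufacture. At 85%:
- expected successes are 0.85 × 15 = 12.75 against 8 needed, or 0.85 × 20 = 17 against 11;
- under replacement, expected Step 0 enrolment for 15 vaccinated is 15/0.85 = 17.6, far below 30.

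Under replacement, the chance of reaching 15 vaccinated within 29 enrolled is P(X ≥ 15 | 29, p). It exceeds 0.999 at p = 0.85, and is 0.86 at p = 0.60 and 0.50 at p = 0.50. The last two rates are assumptions. The documents give no rate from Step 0 to first dose, though Section 10.1 expects some recurrences during vaccine production and administration.

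**The case against.** The strongest reply is that the essentials are already fixed. Section 1.1 gives the criterion and threshold, and 6.3 gives both populations. Replacing a patient means adding another; no section says that the replaced patient leaves the analysis. This stands. A reader might infer that the plan would report 15 of 15, or 100%, as its feasibility result. That follows only if 6.3 is ignored, so it is not a predicted outcome.

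A second reply is that 13.2.1 concerns safety and may mean Step 1 enrolment, which falls close to the first dose. On that reading it agrees with 6.3, so calling it plainly false goes too far. It still does not say so, and 13.1, in the same chapter, uses enrolment for a point before sequencing. The sentence also speaks of DNA vaccines in a peptide trial, which suggests carried-over text, though that is only an inference.

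Third, twenty enrolled to give 15 evaluable is a sensible plan. That is plausible, but no section states it, and the Summary enrols fifteen.

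Fourth, the monitoring reports in Section 12 list how many participants met each objective, and 13.2 is descriptive. The missing feasibility sentence is therefore a gap in detail and would not be a serious fault by itself.

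**Conclusion.** Wrong as written, and minor. Two points are literal and unreconciled: 15 against 20 enrolled, and the enrolment timing in 13.1 against 4.2 and 8. The 13.2.1 sentence conflicts with 4.2, 8 and 6.3 unless it refers to Step 1 enrolment.

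The consequence is that the required count (8 of 15 or 11 of 20) and the reported proportion depend on who counts as enrolled. Stronger conclusions are not supported. The safety set is unaffected, because 6.3 limits it to patients with at least one injection. The safety and immunogenicity calculations reproduce at n = 15 within rounding. The feasible verdict would not change at 85%. That figure covers design and manufacture only, so the conclusion assumes that losses before the first dose do not bring overall success down towards one half.

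**What to change.** 1. State one sample size in the Summary, 13.1 and 13.1.1: 15 vaccinated and evaluable patients, plus the number planned for Step 0 enrolment.
2. Align the enrolment timing in 13.1 with 4.2 and 8.
3. Replace the 13.2.1 sentence with a statement that safety is analysed in patients with at least one injection, as in 6.3.
4. Say in 6.1 and 13.1.1 that patients replaced after Step 0 enrolment stay in the 6.3 feasibility denominator. Keep the term screen failure for those who fail before that enrolment.
5. Add to 13.2 the proportion of Step 0 enrolled patients who meet the 1.1 criterion. An exact 95% interval would be a useful addition.

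The cost is an amendment to wording, with no added patients, visits or assays.

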9.2.2 Sample collection and processing

During Step 0 enrollment, tumor samples will be reviewed by a pathologist with expertise in pancreatic cancer who will review the operative specimen slides to verify tumor cellularity and quantity sufficient for proceeding. Once tissue viability is confirmed, specimens from outside Washington University will be shipped to the [name] lab at the following address: [name] Lab, [name]. The corresponding FFPE blocks will be punched with a disposable 1mm biopsy punch. 6-8 full thickness punches will be taken from areas of high tumor cellularity and divided evenly into two DNA LoBind Eppendorf tubes (one tube for DNA and one for RNA). To identify somatic mutations, DNA and RNA will be extracted from the FFPE preserved tissue by the Center for Human Immunology and Immunotherapy Programs (CHiiPS) core. All tissue selected for sequencing will be processed into a single-cell suspension by mechanical and enzymatic digestion, and used to extract nucleic acids. Tumor DNA + RNA will then undergo tumor exome and tumor cDNA-capture sequencing, respectively at the Genome Institute. Normal genomic DNA will be isolated from PBMCs by the CHiiPS core or [name] laboratory personnel for normal exome sequencing at The Genome Institute.

Patients will undergo their first blood draw during Step 0 screening to establish a baseline for immune monitoring and for creation of the vaccine. This first blood draw will be shipped ambient same day of draw to the [name] lab at the following address: [name] Lab, [name]. Additional optional pre-vaccine blood samples will be obtained midway through chemotherapy and at the end of chemotherapy. Immune monitoring labs will be draw prior to vaccination on Days 1, 22, 50, and 78. Post- vaccine immune monitoring labs will be drawn at the first two follow-up time points (4 weeks after last injection and 1 year after last injection). Seven collection tubes (BD Vacutainer® sodium heparin (green top), REF 367874, 10 mL each for a total of approximately 70 mL) are filled by venipuncture at each time point. Blood samples will be transported to [name]/JHU equivalent laboratory ([name]) within one hour of collection. PBMC will be obtained by Ficoll-Hypaque gradient centrifugation and cryopreserved in 10%

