9.2.3 ELISPOT Analysis

ELISPOT analysis, will be performed as previously described [46-50]. PBMC from subjects in the phase 1b clinical trial will be tested for secretion of IFN- γ by ELISPOT assay. PBMC will be plated at various concentrations starting at 300,000 cells per well, in triplicate, following the protocol previously described by [name] and colleagues. PBMC will be co-cultured with the mutant and mesothelin peptides encoded by the polyepitope construct. As negative controls, PBMC will be incubated in medium alone or stimulated with matching wild type peptides. As a positive control we will include a mix of viral peptides, CEF, containing immunodominant epitopes for multiple common HLA alleles from influenza virus, cytomegalovirus, and Epstein-Barr virus. After 24-48 hours, the plates will be developed and the spots counted in an ImmunoSpot Series I analyzer (Cellular Technology).

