13.2.3 Exploratory objectives

Blood samples will be obtained at multiple time points (prior to vaccination, during, and post-vaccination) in order to procure PBMC for correlative studies. Functional studies will include ELISPOT, T cell poly-functionality by intra-cellular cytokine and degranulation analysis using multi-parametric flow cytometry, as detailed in Section 9.

Time to disease progression will be evaluated with physical examination and diagnostic imaging as clinically indicated. The time to disease progression will be described using Kaplan-Meier product limited method. The median progression-free survival (PFS), median overall survival (OS), and their 95% CIs will be estimated. The association between immunogenicity and PFS or OS will be explored by comparing the survival curves between immune responders versus non-responders. To determine whether the observed difference is larger than might be expected by chance, a permutation test will be used to compare the observed test statistic to the distribution of test statistics that would be seen if there were no difference between the two studies. Specifically, we will randomly shuffle the status of response and calculate the test statistic from the shuffled data. This procedure will be repeated 10,000 times and the resultant testing statistics will provide an accurate representation of the null distribution. The observed test statistics of between-study differences will be compared to the null distributions. For each outcome, the permuted p-value will be the fraction of permuted samples that resulted in a small statistic than the original sample [53].

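### The 2-SD positivity rule leaves its SD undefined and sets no minimum rise; with an SD over triplicate ELISPOT wells, about 7% to 25% of single antigen tests per visit are positive with no vaccine effect

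*Combined protocol and SAP*

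**What the plan says.** Section 13.2.2 gives the rule: "Responses will be considered positive if the number of T cells after vaccination is greater than two standard deviations above the mean before vaccination". It then states its use: "The frequency of positive responses at each time point will be assessed and binomial response rates with 95% confidence interval estimates will be presented". Section 13.2.3 reuses the label by "comparing the survival curves between immune responders versus non-responders" for PFS and OS.

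The data behind the rule are described in section 9.2. On ELISPOT replication, 9.2.3 says: "PBMC will be plated at various concentrations starting at 300,000 cells per well, in triplicate". On controls: "As negative controls, PBMC will be incubated in medium alone or stimulated with matching wild type peptides". The positivity rule does not refer to those controls.

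On sampling, 9.2.2 takes a first draw at Step 0 and adds: "Additional optional pre-vaccine blood samples will be obtained midway through chemotherapy and at the end of chemotherapy". It continues: "Immune monitoring labs will be draw prior to vaccination on Days 1, 22, 50, and 78". After vaccination, "immune monitoring labs will be drawn at the first two follow-up time points". That makes two to four pre-vaccination draws and up to five post-vaccination looks (Days 22, 50 and 78, 4 weeks, 1 year).

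The plan does not state which SD is meant, what happens when it is zero, what minimum rise is required, or how peptides, visits and the two assays combine into one call per patient. Section 13.2 describes the analysis as descriptive.

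**The concern.** A mean-plus-2-SD limit has a tail of 2.3% only when the mean and SD are known and the data are normal. Here both may be estimated from as few as two or three values, and ELISPOT data are counts. Baseline wells of 0/0/0 have mean 0 and SD 0, so the threshold is 0 and a post-dose 0/0/1 counts as a response. Baseline 1/1/1 followed by 1/1/2 also counts, since the SD is again 0 and 1.33 exceeds 1.

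A response rate with a confidence interval will be read against zero. If the rule gives a rate well above zero with no vaccine effect, that reading misleads. The same false calls blur the responder split used for PFS and OS. Because the SD source is open, it could also be chosen after the data are seen.

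**Working it through.** **Inputs from the documents.** Three wells per condition (9.2.3); two to four pre-vaccination draws (9.2.2); 15 evaluable patients and a CV of about 20% (13.1.3); up to four pools of up to four peptides, so up to 16 (5.1.4).

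**Assumptions.** Baseline spots per well, λ, is not given and is varied. Counts are Poisson with the same λ before and after. One antigen test is counted at a time.

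**1. The plan's nearest figure.** Section 13.1.3 gives 80% power for a 0.68 SD increase (paired t-test, n=15, one-sided 0.05). With correlation 0.5 the SD of the difference equals SD, the noncentrality is 0.68 × √15 = 2.63, and power is 80.5%. The figure reproduces. Also 0.68 × 20% = 13.6%, which the plan rounds up to 15%. This calculation concerns mean change. The plan states no error rate for the positivity rule.

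**2. Normal data, no effect.** With m0 baseline and m1 post-dose values, P(positive) = P(t on m0−1 df > 2/√(1/m0 + 1/m1)).

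| SD taken over | m0, m1 | cut-off | rate |
|---|---|---|---|
| triplicate wells | 3, 3 | 2.449 | 6.7% |
| two draws | 2, 1 | 1.633 | 17.5% |
| three draws | 3, 1 | 1.732 | 11.3% |
| four draws | 4, 1 | 1.789 | 8.6% |
| 15 patients | 15, 1 | 1.936 | 3.7% |

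**3. Poisson counts, SD over triplicate wells.** The 0/0/0 route alone contributes e^(−3λ) × (1 − e^(−3λ)). This peaks at 25% when e^(−3λ) = 0.5, that is λ = ln 2 / 3 = 0.23. Simulation (300,000 to 400,000 runs per row) gives the total:

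| λ | baseline 0/0/0 | via 0/0/0 | total per visit |
|---|---|---|---|
| 0.02 | 94% | 5.5% | 5.5% |
| 0.05 | 86% | 12.0% | 12.0% |
| 0.1 | 74% | 19.2% | 19.2% |
| 0.25 | 47% | 24.9% | 25.0% |
| 0.5 | 22% | 17.3% | 18.3% |
| 1 | 5% | 4.7% | 10.7% |
| 5 | 0% | 0% | 8.0% |
| 20 | 0% | 0% | 7.3% |

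**4. Other readings.** SD across 15 patients, Poisson, λ from 0.05 to 20: about 4 to 9%. Six pooled baseline wells from two draws: 2 to 14%. Triplicate wells with an added 20% draw-to-draw CV, λ from 1 to 100: 12 to 29%.

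**5. Accumulation.** Any of five visits, triplicate reading: 18% (λ = 100) to 52% (λ = 0.2). Any of 4 or 16 independent peptides at 6.7% each: 1 − 0.933^4 = 24%; 1 − 0.933^16 = 67%.

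**6. At n=15, one test per patient.** Expected false responders per visit: 15 × 0.067 = 1.0 and 15 × 0.25 = 3.75.

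**7. Candidate repairs.**
- Positivity at two given visits: about 3% at λ of 5 or more, but 11 to 13% at λ of 0.2 to 0.5, because both visits share one baseline.
- Exact two-Poisson test at one-sided 0.025: near 2% with pure Poisson noise, but 13% at λ = 20 and 22% at λ = 50 with a 20% draw-to-draw CV.
- The 2-SD rule plus a rise of at least 5 spots per well and at least twice baseline: at or below 0.8% with Poisson noise and 3.8% with the 20% CV. These runs used gross counts, without background subtraction.

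**The case against.** A reader might infer that the rule, as written, labels 7 to 25% of patients as responders at each visit. The documents do not support that.

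- **SD source.** Section 13.2.2 never ties the SD to wells or draws. The same paragraph summarises each time point by means and SDs, so an across-patient SD is admissible. It gives lower rates, and a zero threshold would then need all 15 baselines to be zero. This stands. It is a weak choice all the same: each patient has different peptides, so that SD mixes antigens and ignores the patient's own baseline.
- **Low baselines.** Nothing shows that 0/0/0 is typical. Under Poisson noise the plan's 20% CV would need 1/0.2² = 25 spots per well, or about 8 if it describes a triplicate mean, where the rate is 7 to 8%. But the plan does not say what the 20% measures. Section 2.7 also favours epitopes that already stain with tetramer, which works against near-zero counts. The 25% end is therefore conditional.
- **Assay.** The triplicate argument covers ELISPOT only. Sections 9.2.4 and following give no replicates for flow cytometry, which is read after ten days of culture.
- **Cited source.** The rule cites a method paper that may settle the SD or the background handling. That cannot be checked here, and the plan should state the rule itself.
- **Importance.** The endpoint is powered on mean change, and 13.2.2 also calls for continuous summaries and distributions, so a 0/0/1 responder could be noticed. This limits the harm but does not repair a reported rate and interval.

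**Conclusion.** The concern holds in conditional form. The rule lacks an SD definition, a minimum rise, a background criterion and a confirmation step. With the SD over one set of triplicate baseline wells, the no-effect rate per antigen test and visit is about 7% at moderate counts and up to about 25% at about 0.2 to 0.25 spots per well. It falls again at still lower counts (5.5% at 0.02). The figures rest on Poisson counts and assumed baselines. Across the readings examined, the rate for one test runs from about 2% to 29%, so leaving the SD open is itself a defect. Converting a per-test rate into a share of patients needs a rule for combining peptides and visits, which the plan does not give.

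The effect is confined to the secondary response rate and the exploratory PFS/OS split. The primary safety and feasibility objectives are untouched.

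**What to change.** In 13.2.2, keep a within-patient comparison and:

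1. State the SD source (which wells, which draw or draws) and what applies when the SD is zero.
2. Require a numeric minimum rise and a fold-change over the patient's own pre-vaccination value, both net of the medium-alone wells already planned. Fix both before the batched assays are run. A floor of 5 spots per well and twice baseline illustrates the gain. At 300,000 cells per well, 5 spots is 5/0.3 = 16.7 per million PBMC. The laboratory should set the actual values from its own background and draw-to-draw variation.
3. State how peptides and visits combine into the single patient label used in 13.2.3, and give flow cytometry its own criterion.
4. Report the rule's no-effect rate beside the response rate and its interval.

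Neither two-visit confirmation nor an exact two-Poisson test should carry the rule alone, for the reasons in step 7 of the working.

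The cost is SAP wording, with no new samples or assays. The downside is that very small rises no longer count. For example, a true rise from 0.5 to 5 spots per well averages 4.5, below the illustrative floor, and would be missed more often than not. The continuous summaries already planned would still show such rises.
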